## Study Protocol and Data Analytic Plan

### 1. Brief Description of Protocol

#### 1.1 Protocol Overview

The aim of this study is to compare the effects of DBT emotion regulation skills training (DBT-ER), DBT interpersonal effectiveness skills training (DBT-IE), and an evidence-based interpersonal process (IP) support group developed by [name] on emotional functioning and on BPD-related outcomes. These targets will be assessed using innovative laboratory-based assessment methods. This study uses an NIH Phase III randomized clinical trial to parse the link between elements of DBT skills training modules to specific mechanisms of action. Participants are adults with 4+ BPD criteria and recent, recurrent self-injurious behaviors ( $N = 81$ ). The interventions under study are:

- An orientation meeting plus 6-week DBT-ER skills training group,
- An orientation meeting plus 6-week DBT-IE skills training group, and
- An orientation meeting plus 6-week IP support group

Theorized mechanisms and outcomes will be assessed via self-report and laboratory assessment at baseline (week 0-1), mid-treatment (week 3-4), and post-treatment (week 6-7), and follow-up questionnaires will be administered (week 13-14).

Participants were randomized via the Redcap randomization module, stratified by reported emotion regulation difficulties (above/below 106.87,) the lower end of the cutoff in previous research, and gender.

#### 1.2 Methods Summary

Self-report measures will be assessed at baseline, mid-treatment (week 3-4), post-treatment (week 6-7), and follow-up (week 13-14). Primary (namely BPD symptoms on the Borderline Symptom List, BSL, emotion dysregulation on the Difficulties in Emotion Regulation Scale, DERS,) and Secondary (DBT skills use on the DBT-WCCL,) self-report p|outcomes are indicated below, although additional measures will also be included. Laboratory-based paradigms will be assessed at baseline, mid-treatment, and post-treatment.

### 1.2.1 Deliberate Emotion Regulation Laboratory Paradigm

Standardized scripts will be used to assess deliberate emotion regulation, based on past work . Scripts are approximately 4 sentences, written in second-person ranging 45-50 seconds in length, used in past research with BPD samples (; ). We first evaluate baseline responses with a recorded neutral mood induction script (selected randomly of 3 standard scripts). Participants continue to sit for another 90-120s after each script (; ), while physiological measures (skin conductance, heart rate variability) are recorded. Participants then listen to 2 recorded negative scripts (randomly selected from 6 total scripts that elicit comparable negative valence/arousal in BPD samples). Per past research , participants are instructed to either *maintain* (i.e., respond as they normally would) or *decrease* (i.e., adopt a third-person, detached view) their emotions while listening to the negative scripts. Instruction order is counterbalanced.

### 1.2.2 Automatic Emotion Regulation Laboratory Paradigm

To evaluate “automatic emotion regulation”, we will use an established paradigm used in BPD samples. Startle eye-blink is assessed, and participants wear headphones throughout. Participants are presented with negative and neutral images (primarily social from the IAPS used in BPD samples), with some images presented twice, permitting an examination of Repeated vs. Novel images, consistent with past work in BPD. A subset of images in each Valence (Neutral, Negative) and Stimulus Type (Novel vs. Repeated) were accompanied by a startle-eliciting probe (105 dB sound pressure level white noise 50ms long). Unique images matched for valence/arousal will be counterbalanced and used at each lab session. EMG will be used to assess startle amplitude, permitting an examination of affect-modulated startle.

## 2. Data Analytic Plan

### 2.1 Preliminary Analyses

Preliminary analyses will examine descriptive data to examine distributional properties of each variable. Transformations (e.g., log transformations) will be applied for variables not meeting normality assumptions. Alternative models (e.g., Poisson or negative binomial) will be used for variables that are not sufficiently normalized by these transformations, as appropriate. Extreme outliers will be considered and adjusted if necessary.

We will consider data missingness. If the data are in fact missing not completely at random, we may only include the ITT sample that also completed at least one of the follow-up timepoints. If data are MAR, we will use Full Information Maximum Likelihood Estimation (FIML),

Preliminary analyses will examine the effectiveness of the lab-based manipulations in the paradigms, to check that the hypothesized emotion induction manipulations operated as expected.

Covariates will be considered per analysis. We will consider including covariates that show associations with the dependent variables (DVs) in analyses particularly if they differ across conditions, including demographic variables, baseline measures of the variables of interest ((and BMI and medication in analyses of physiological variables). Given the small sample size, nonsignificant variables in models may be trimmed from final model reporting.

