## 2.2 Primary Analyses

Given that most of these outcomes will be assessed at Weeks 0 (baseline), 3-4, 6-7, and 13-14, for most primary analyses we will use mixed effects models. We plan to evaluate whether the data are appropriate for use of multilevel models which account for the interdependence of multiple repeated measures within individuals, using full maximum likelihood estimation. Consistent with recommended practices, we will consider a series of models to test how to consider time, levels, and which (if any) random effects to include. If such models do not accurately capture the data, we may resort to single-level regressions. In addition, it is important to consider variability in the group clusters, which is a key strength of using multilevel model analyses to model complex change over time. Given the restraints on sample size imposed by the scope of this proposal, we opted to minimize group-level variability across groups and therapists by retaining the same DBT therapists across the DBT-ER and DBT-IE conditions. Likewise, across all control groups, we will retain the same therapists. We will consider whether to model variability at the level of groups. Alpha will be set to .05 for primary pre-specified outcomes without error correction given the small sample size.

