### 2.2.1 Primary Outcomes

We will examine the effect of condition (DBT-ER, DBT-IE, IP) on (1a) BPD (as measured by the BSL,) and (1b) emotion regulation (as measured by the DERS,). These outcomes were assessed at baseline mid-treatment, post-treatment, and follow-up. We will examine change slopes within each condition and test how these slopes differ.

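### Section 2.1 leaves the analysis set for BSL and DERS open: an optional exclusion of randomised participants has a trigger that observed data cannot settle

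*Combined protocol and SAP*

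**What the plan says.** Missing data are covered in one short paragraph of section 2.1 (Preliminary Analyses). It opens with "We will consider data missingness" and then gives two conditional statements:

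- An optional exclusion, if data are "missing not completely at random, we may only include the ITT sample that also completed at least one of the follow-up timepoints".
- A choice of estimator, in the sentence that follows: "If data are MAR, we will use Full Information Maximum Likelihood Estimation (FIML").

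The first concerns who is analysed and is optional. The second concerns how the model is estimated, is worded as a commitment, and names no analysis set. ITT appears only here and is not defined.

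Section 2.2 plans "multilevel models which account for the interdependence of multiple repeated measures within individuals, using full maximum likelihood estimation" but states no population. It also keeps a fallback: "If such models do not accurately capture the data, we may resort to single-level regressions". Section 2.2.1 lists baseline with the three later assessments of BSL and DERS and says: "We will examine change slopes within each condition and test how these slopes differ". On covariates, section 2.1 will consider baseline measures, but "nonsignificant variables in models may be trimmed from final model reporting".

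**The concern.** Not MCAR covers both MAR and MNAR. Read literally, MAR data therefore meet both conditions in section 2.1. No test, decision time or order of precedence is given, and neither approach is labelled primary or sensitivity. Two analysts following the plan could analyse different sets of people for the same primary outcome.

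The exclusion also conditions on something that happens after randomisation, namely returning for a later assessment. It is allowed in the situation where it can do harm: when loss is not completely at random, those who return may differ from those who do not. If they differ at baseline, removing the others shifts the baseline mean of the retained group, and regression to the mean then shows up as part of the slope. Section 2.2.1 makes both the within-condition slopes and their differences targets, so both are exposed. The full maximum likelihood planned in section 2.2 can keep people who have only a baseline score.

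**Working it through.** **Step 1: the two conditions side by side.**

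| Mechanism | Exclusion sentence | FIML sentence |
|---|---|---|
| MCAR | not triggered | not addressed by name |
| MAR | triggered (*may*) | triggered (*will*) |
| MNAR | triggered (*may*) | not triggered |

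If the wording of the exclusion sentence is a slip for MNAR, the overlap in the MAR row goes. The exclusion is still optional, and observed data cannot separate MAR from MNAR.

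**Step 2: inputs for an illustration.** The plan has no figure on this point to reproduce. From the documents: N = 81 in three conditions, with assessments at week 0 and weeks 3-4, 6-7 and 13-14, taken as 0, 3.5, 6.5 and 13.5. Assumed: equal allocation (81/3 = 27 per arm), SD 1 and correlation 0.6 between all visits, no true effect, and a straight-line slope per arm with baseline as an outcome occasion. Loss means no post-baseline visit at all, with log-odds of loss 1.0 per baseline SD.

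**Step 3: from retained baseline mean to slope.** The mean time is 5.875 weeks and the sum of squares about it is 98.69. If the retained group has baseline mean m, its expected scores are m × (1, 0.6, 0.6, 0.6). The fitted slope over 13.5 weeks is then

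13.5 × m × (−5.875 × 1 + 5.875 × 0.6) / 98.69 = −0.3215 × m.

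Numerical integration gives m, and hence the within-condition bias:

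| Loss | m (SD) | Slope bias over 13.5 weeks (SD) |
|---|---|---|
| 10% | −0.091 | 0.029 |
| 15% | −0.133 | 0.043 |
| 20% | −0.173 | 0.056 |
| 30% | −0.253 | 0.081 |

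**Step 4: between-condition bias.** Subtract the two within-condition biases if high scorers are lost in both arms (same direction). Add them if high scorers are lost in one arm and low scorers in the other (opposite). SE = 13.5 × √(0.4/98.69 × (1/n1 + 1/n2)), with n the number retained per arm. At 10%/30%, n = 24.3 and 18.9, so SE = 0.264.

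| Loss by arm | Direction | Bias (SD) | SE | Bias/SE |
|---|---|---|---|---|
| 20%/20% | same | 0.000 | 0.26 | 0.00 |
| 15%/20% | same | 0.013 | 0.26 | 0.05 |
| 10%/20% | same | 0.027 | 0.25 | 0.10 |
| 10%/30% | same | 0.081 − 0.029 = 0.052 | 0.26 | 0.20 |
| 10%/30% | opposite | 0.081 + 0.029 = 0.110 | 0.26 | 0.42 |
| 20%/20% | opposite | 0.056 + 0.056 = 0.111 (unrounded inputs) | 0.26 | 0.43 |

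Loss of 10%/30% unrelated to baseline gives 0.000. The 10%/30% range of 0.052 to 0.110 becomes 0.065 to 0.138 at correlation 0.5, 0.039 to 0.083 at 0.7, and 0.026 to 0.055 at 0.8.

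**Step 5: full maximum likelihood on all randomised.** When the fitted covariance matches the one generating the data, its bias under MAR is zero. That is not general. In a large-sample calculation at 10%/30% loss, the correlations with baseline were assumed to decay over the three later visits (0.84, 0.72, 0.50, or about 0.6, 0.5, 0.33):

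| Fitted model | All randomised | Restricted set |
|---|---|---|
| Random intercept only | about 0.03 to 0.09 SD | about 0.08 to 0.2 SD |
| Random intercept and slope | 0.01 SD or less | about 0.08 to 0.2 SD |

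**Step 6: MNAR.** At 10%/30%, same direction, loss driven by the week-13.5 score gives −0.068 SD restricted against −0.099 full maximum likelihood. Loss driven by change to week 13.5 gives −0.135 against −0.112. Both options are biased, and each is the better one once.

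**The case against.** The strongest case for the plan has five parts.

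- *The sentences may not conflict.* The contrast with MAR suggests that the exclusion was meant for MNAR, and *will* reads more firmly than *may*. One sentence sets a population and the other an estimator, so FIML could be run on either set. All this is fair. A reader might infer a flat contradiction, and the documents do not support that. What stands is an optional exclusion whose trigger cannot be established.
- *Baseline may be only a covariate.* Section 2.1 lists baseline measures as candidate covariates. If only later scores are outcomes, participants with baseline alone contribute nothing and the two sets nearly coincide. The slope wording in section 2.2.1 makes baseline as an outcome occasion the natural reading but does not settle it.
- *Full maximum likelihood is not automatically safe.* A reader might infer that it is unbiased whenever data are MAR. Step 5 shows that this needs an adequate covariance, and section 2.2 leaves the random effects to be chosen. The restricted set was still worse in each case computed. Likewise, baseline adjustment in the single-level fallback removes only bias from baseline-driven loss. It does not remove bias from loss that depends on mid- or post-treatment scores.
- *The harm is small.* This stands. Larger figures need harsher assumptions: 10%/40% loss with log-odds 1.5 gives 0.098 to 0.176 SD against a standard error of 0.28. Unequal loss alone, unrelated to baseline or outcome, does no harm.
- *The term follow-up timepoints is unclear.* Elsewhere follow-up means the week 13-14 assessment. The figures above take it as any post-baseline visit. The narrow reading could exclude more people, and its size was not computed.

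**Conclusion.** The concern holds in a limited form. Section 2.1 leaves the analysis set for both primary outcomes undecided until the data are seen, whether its exclusion sentence is read literally or as a slip for MNAR. One permitted option can bias the slopes under MAR. Within conditions the bias is about 0.06 SD at 20% baseline-related loss. Between conditions it is 0.00 to 0.03 SD for loss up to 10%/20% with the same mechanism and 0.05 to 0.11 SD at 10%/30%, with a standard error of about 0.26. These sizes rest on assumed loss rates, a correlation of 0.6, 27 per arm and baseline as an outcome occasion.

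The documents do not support saying that the exclusion would materially change the trial's conclusions, or that full maximum likelihood solves the problem under MNAR. The argument is mainly one of pre-specification: the better default is already planned and costs almost nothing to fix in place. It should be corrected.

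**What to change.** In section 2.1, delete the restriction as a primary-analysis option. In sections 2.2 and 2.2.1:

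1. Name one primary analysis for BSL and DERS, whatever a missingness test shows: the full-maximum-likelihood mixed model on all randomised participants, with baseline as an outcome occasion.
2. Specify a covariance structure not limited to a random intercept, for example a random slope or an unstructured covariance, where estimable.
3. If the single-level fallback is used, keep baseline as a covariate that cannot be trimmed, and note that this deals with baseline-driven loss only.
4. Define follow-up timepoints (any post-baseline visit, or week 13-14 only) and report that subset only as a baseline-adjusted sensitivity analysis.

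A delta-adjustment analysis for MNAR is optional.

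The cost is a few lines of SAP text and a little more analysis for each primary outcome. No new data are needed. With 27 per arm, a richer covariance may not always be estimable, so the plan should state the order in which simpler structures will be tried.

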## 2.2 Primary Analyses

Given that most of these outcomes will be assessed at Weeks 0 (baseline), 3-4, 6-7, and 13-14, for most primary analyses we will use mixed effects models. We plan to evaluate whether the data are appropriate for use of multilevel models which account for the interdependence of multiple repeated measures within individuals, using full maximum likelihood estimation. Consistent with recommended practices, we will consider a series of models to test how to consider time, levels, and which (if any) random effects to include. If such models do not accurately capture the data, we may resort to single-level regressions. In addition, it is important to consider variability in the group clusters, which is a key strength of using multilevel model analyses to model complex change over time. Given the restraints on sample size imposed by the scope of this proposal, we opted to minimize group-level variability across groups and therapists by retaining the same DBT therapists across the DBT-ER and DBT-IE conditions. Likewise, across all control groups, we will retain the same therapists. We will consider whether to model variability at the level of groups. Alpha will be set to .05 for primary pre-specified outcomes without error correction given the small sample size.

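### Reported mixed-model inference rests on full maximum likelihood with no small-sample degrees of freedom: a small cost at participant level, a material one if a therapy-group effect is fitted

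*Combined protocol and SAP*

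**What the plan says.** Section 2.2 of the combined protocol and SAP proposes "multilevel models which account for the interdependence of multiple repeated measures within individuals", "using full maximum likelihood estimation". REML is not mentioned anywhere. Nor is a reference distribution or a degrees-of-freedom method for the tests.

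The random-effects structure is left to the data: "we will consider a series of models to test how to consider time, levels, and which (if any) random effects to include". All three conditions are delivered in groups (section 1.1; for example "An orientation meeting plus 6-week DBT-ER skills training group"). On clustering by group, section 2.2 says only: "We will consider whether to model variability at the level of groups". The mitigation offered is to "minimize group-level variability across groups and therapists by retaining the same DBT therapists across the DBT-ER and DBT-IE conditions", with the control groups likewise keeping their own therapists.

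The sample is 81 in three conditions (section 1.1). Section 2.2 sets alpha at .05 for the primary outcomes with no multiplicity correction. The primary contrast is the difference between conditions in change slopes (section 2.2.1).

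**The concern.** Full ML estimates variance components as if the fixed effects were known, so the components are biased downward. The bias depends on how many independent units carry the treatment contrast. With 81 participants it is slight. With therapy groups as the units it can be large, because 81 people in three group-treated arms probably form few groups. A z reference adds to the problem by ignoring the uncertainty in the estimated variance.

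At stake is the error rate of the condition comparisons on the BSL and the DERS. These already run at .05 each without correction, so there is no slack to absorb inflation. A group variance biased toward zero is also easier to drop when random effects are chosen from the data.

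**Working it through.** The plan states no power calculation, ICC or number of groups, so there is no figure of its own to reproduce.

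**Inputs from the documents:** N = 81; 3 conditions; alpha .05; full ML; group delivery.

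**Assumptions:** two-sided tests; equal allocation (about 27 per arm); a z reference for the ML tests; 9, 12 or 15 groups in total; group ICC for change of 0, 0.05 or 0.10.

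**1. Participant level.** For balanced data with three arm-specific slopes and m independent units, ML variance / REML variance = (m − 3)/m.
- m = 81: 78/81 = 0.963. The SE ratio is √0.963 = 0.981, so SEs are about 2% low.
- Type I error of ML with z: 2·P(t₇₈ > 1.96 × 0.981) = 5.8%.
- Interval width against REML with t₇₈: 1.96 × 0.981 / 1.991 = 0.966, which is 3.4% narrower.
- Check: 150 simulated trials were fitted with random intercept and slope (81 participants, 4 visits, assumed 20% dropout). The median SE ratio was 0.978.

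**2. Group level, limiting case.** When variation between groups dominates, the same formula holds with m = G groups, and type I error is 2·P(t₍G−3₎ > 1.96·√((G − 3)/G)).

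| Groups | Variance ratio | SE ratio | Type I error, ML with z |
|---|---|---|---|
| 9 | 0.67 | 0.82 | 16.1% |
| 12 | 0.75 | 0.87 | 12.4% |
| 15 | 0.80 | 0.89 | 10.5% |

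These are upper limits, not expected values.

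**3. Group level, realistic ICCs.** This used 200,000 simulated trials per setting, groups nested in three arms, one change value per participant, and a pairwise arm contrast. With k groups of n per arm, SE² = 2·MSB/(kn), where MSB is SSB/G under ML and SSB/(G − 3) under REML. When the group variance is estimated as zero, the pooled mean square replaces MSB. The last column omits the group effect and uses REML with participant-level t.

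| Groups × size per arm (total) | ICC | ML, z | REML, z | REML, t(G−3) | Group omitted |
|---|---|---|---|---|---|
| 3 × 9 (81) | 0 | 5.4% | 4.1% | 1.2% | 5.0% |
| | 0.05 | 9.1% | 6.4% | 2.5% | 9.9% |
| | 0.10 | 11.8% | 7.8% | 3.4% | 14.8% |
| 4 × 7 (84) | 0 | 5.3% | 4.2% | 2.0% | 5.0% |
| | 0.05 | 8.0% | 5.9% | 3.2% | 8.7% |
| | 0.10 | 9.8% | 7.0% | 3.9% | 12.4% |
| 5 × 5 (75) | 0 | 5.3% | 4.3% | 2.6% | 5.0% |
| | 0.05 | 7.2% | 5.6% | 3.5% | 7.5% |
| | 0.10 | 8.5% | 6.4% | 4.1% | 10.0% |

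The 84 and 75 totals are the nearest balanced layouts to 81. Repeat runs agreed within about 0.2 points. With 9 groups and a true group variance of 0.10, the mean estimate was 0.048 under ML and 0.107 under REML.

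**4. Which ingredient matters.** With 9 groups and ICC 0.10, ML with z gives 11.8%. Changing only the estimator gives 7.8%, a fall of 4.0 points. Changing only the reference, to ML with t(6), gives 5.6%, a fall of 6.2 points. Both contribute, and the missing degrees of freedom contribute more.

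**The case against.** A reader might infer that full ML, as planned, makes this trial's intervals materially too narrow because there are few groups. The documents do not support that as a fact. The number and size of groups are not stated. The ML phrase is attached to repeated measures within participants, where the effect is small. The larger figures need three things the plan does not settle: a fitted group random effect, a non-zero group ICC and a z reference. At ICC 0, ML with z is close to nominal. Retaining therapists may also lower the ICC, though it does not remove effects of shared membership. All of this stands.

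It can also be said that ML is not the main culprit. In the same layouts, ML with t(G−3) gives 3.7%, 4.4% and 4.5% at ICC 0.05 and 5.6%, 5.8% and 5.7% at ICC 0.10. That is nearer 5% than REML with t(G−3) in all six cases. The figures stand, but the closeness comes from two errors that offset each other: a variance biased downward and a fixed reference that is conservative when group variance is small. The balance already tips above 5% at ICC 0.10. It does support treating degrees of freedom as at least as important as the estimator.

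Finally, REML alone would miss the larger risk. If the group effect is left out, which the plan permits, inflation is as large as or larger than under ML with the group effect fitted. This stands and shapes the fix.

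**Conclusion.** The point holds in a conditional form. The plan names full ML and no small-sample degrees of freedom. For the models it commits to, this is slightly anticonservative. If the optional group effect is fitted, type I error with a z reference would be about 7 to 12% across the assumed ICCs of 0.05 and 0.10 and 9 to 15 groups, and near nominal if the ICC is zero. Group counts, ICCs, equal allocation and the z reference are assumptions. The simulation uses one change value per participant rather than the full four-visit model. The direction is secure; the size depends on facts the sponsor holds. The correction is cheap and worth making, provided that it also settles the group effect.

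**What to change.** For the Gaussian mixed models only, replace the estimation wording in section 2.2 with:

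> *Full ML is used only to compare nested models that differ in fixed effects. Reported estimates, confidence intervals and p-values for the Gaussian mixed models come from REML with Kenward-Roger or Satterthwaite degrees of freedom, and the primary models include a therapy-group random effect on change.*

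Delete the sentence that leaves group-level modelling open, and state the number of groups. The Poisson or negative binomial models, latent growth curve models and single-level regressions mentioned elsewhere in the plan need their own statement, since this wording does not carry over to them. REML uses all available visits under MAR, so it fits the likelihood-based handling of missing data in section 2.1.

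The drafting cost is a sentence and a software option. The statistical cost is wider intervals and some loss of power, which has not been quantified here. The test also becomes conservative when group variance is near zero: REML with t on groups minus 3 df gives about 1 to 3% at ICC 0 and 2.5 to 3.5% at ICC 0.05. Kenward-Roger itself was not simulated. A rough Satterthwaite-type rule in the same layouts, using t(G−3) when the group variance estimate is positive and participant-level df when it is zero, gave 4.2 to 4.9% at ICC 0.05 and 0.10, so a method that adapts its df should be less conservative than the fixed reference.

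### The single-level fallback for BSL and DERS does not say how correlation among a person's four visits is kept; a marginal repeated-measures model would close the gap

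*Combined protocol and SAP*

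**What the plan says.** Section 2.2 plans "multilevel models which account for the interdependence of multiple repeated measures within individuals, using full maximum likelihood estimation". The stated reason for the choice is therefore within-person dependence. The same paragraph then allows an alternative: "If such models do not accurately capture the data, we may resort to single-level regressions". No data layout, standard-error method or marginal covariance model is given for it.

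The fallback covers the primary outcomes, BSL and DERS. Section 2.2.1 states: "These outcomes were assessed at baseline mid-treatment, post-treatment, and follow-up". The primary question is also set there: "We will examine change slopes within each condition and test how these slopes differ". On error rates, section 2.2 says: "Alpha will be set to .05 for primary pre-specified outcomes without error correction given the small sample size".

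The other place where the plan speaks of a single level is section 2.2.2. There it allows data to be collapsed, with startle difference scores and a post-treatment count of self-injury or attempts as the examples. BSL and DERS are not among those examples.

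**The concern.** A random-effects model can fail because it does not converge, because a variance is estimated at zero, or because the time course is not linear. None of these makes four scores from one person independent. As written, the fallback gives up the property for which the main model was chosen and puts nothing in its place.

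If visits were entered as independent rows, stable differences between people would go into the error term of a comparison that is made within people. With a total of 81 participants, a real difference in slopes could be missed only because the fallback was used. Under other covariance patterns the error rate could instead exceed the stated 5%.

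**Working it through.** The plan gives no power, effect size, SD, within-person correlation or dropout figure, so there is no stated result to reproduce.

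**Inputs from the documents.** Total 81 in three conditions (section 1.1); alpha 0.05 and four visits (section 2.2); difference in slopes as the primary test (section 2.2.1).

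**Assumptions.** 27 per arm; visits at weeks 0.5, 3.5, 6.5 and 13.5 (midpoints of the windows in section 1.1); complete data; total SD 1; one arm diverging linearly by 0.6 SD over the 13 weeks from first to last visit. With equal arms, two arms diverging together from the third gives the same result. Therapy-group clustering is not modelled.

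**Size when visits are stacked.** The mean visit time is 24/4 = 6, so Sxx = 5.5² + 2.5² + 0.5² + 7.5² = 93. Under exchangeable correlation ρ, a person's slope has true variance (1−ρ)/93. Stacked least squares reports about 1/93 per person, which is too large. The true size of the 2-df test is therefore approximately P(χ²₂ > 5.991/(1−ρ)) = 0.05^(1/(1−ρ)).

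**Power of the per-person slope test.** The slope difference is d = 0.6/13 = 0.04615 SD per week. The noncentrality is 27 × (2/3) × d² × 93/(1−ρ) = 3.57/(1−ρ), which is 5.09, 7.13 and 11.89 at ρ = 0.3, 0.5 and 0.7. Power comes from the noncentral F with 2 and 78 df. Power for stacked rows was simulated.

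| ρ | Stacked size, formula | Stacked size, simulated | Stacked power | Per-person slope power |
|---|---|---|---|---|
| 0.3 | 1.4% | 1.4–1.6% | 31–32% | 49–50% |
| 0.5 | 0.25% | 0.3–0.5% | 27–28% | 65–66% |
| 0.7 | 0.005% | 0.03% or less | 19–20% | 87% |

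The per-person slope test kept its size at about 5% throughout.

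**Other covariance patterns, stacked rows (simulated).**
- AR(1) of 0.3 to 0.5 per 3.5 weeks: size about 5–6%, and no loss of power (38–39% against 34–35%).
- AR(1) of 0.7: size about 3%. AR(1) of 0.85: about 0.4%.
- Modest random slopes (SD 0.3 to 0.6 by week 13.5): size 0.2–0.8%.
- Large random slopes (SD 2.0 by week 13.5, or 2.0/13.5 = 0.15 per week): size 7–14%.

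**One row per person, using two visits.** At ρ = 0.5 the variance of a change score is 2 × (1−0.5) = 1.
- Baseline to post-treatment: the divergence reached is 0.6 × 6/13 = 0.277, the noncentrality is 18 × 0.277² = 1.38, and power is about 16%.
- Baseline to follow-up: the noncentrality is 18 × 0.6² = 6.48 and power is about 60%.

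Both tests have correct size. What is lost depends on the visit chosen.

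**The case against.** The strongest reply is that the plan never says the visits would be stacked. The fallback is optional, and the plan's examples in section 2.2.2 all collapse data rather than stack rows. A regression of each person's fitted slope on condition is a single-level regression. It uses all four visits, has correct size and answers the question in section 2.2.1. With complete data, a slope contrast with least-squares weights from an unstructured marginal model gives the same estimate. This stands. A reader might infer that single-level regression must treat visits as independent, or that every single-level form is inferior; neither follows from the documents.

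The size of the damage also rests on a covariance that the plan does not report. This stands too: stacking can be harmless, conservative or anticonservative.

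A reader might further infer that the fallback inflates false claims about average level between conditions. Stacked rows would do that under positive correlation, but section 2.2.1 compares slopes and no contrast of average level is specified, so this is not a risk to the primary test as planned. Nor can it be said that a one-row analysis would necessarily drop people with a missing visit, because section 2.1 plans FIML under MAR without limiting it to multilevel models.

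The reply does not close the gap. The collapsing examples concern other outcomes, and the per-person slope is not named anywhere. The text leaves open a valid analysis, a valid but possibly much weaker one, and a mis-sized one.

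**Conclusion.** The concern holds in limited form. For both primary outcomes the plan allows a fallback that does not state how dependence among the four visits is kept. If rows are stacked and correlation is roughly exchangeable at 0.3 to 0.7, the slope test is conservative, and power for a 0.6 SD divergence falls by about 18 to 67 percentage points against a per-person slope test. Under other plausible or more extreme patterns the size is near nominal or too high. If one row per person is meant, the test is valid; a per-person slope keeps the planned question, while a baseline-to-post-treatment change would have little power.

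These figures assume 27 per arm, complete data and covariances that the documents do not give. They show what the wording permits and do not predict the trial's result. The point is a cheap improvement to an optional step: a fallback that uses all visits and respects their correlation is better than the one written.

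**What to change.** In section 2.2, replace the sentence "If such models do not accurately capture the data, we may resort to single-level regressions" with:

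> If the random-effects models do not converge or fit poorly, BSL and DERS will be analysed with a marginal repeated-measures model (all four visits, categorical visit, condition-by-visit, unstructured within-person covariance, small-sample degrees of freedom). The slope contrast will be formed from the visit means. Repeated scores will not be analysed as independent rows.

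A regression of each person's slope on condition may be added as a sensitivity analysis, with a rule for people who have incomplete visits.

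The cost is a sentence or two of SAP text, with no new data or participants. The unstructured covariance has 4 × 5/2 = 10 parameters per outcome, a few more than a simple random-effects model, and is estimable with 81 participants.
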